#### Safety follow-up period

The safety follow-up period applies to the following participants:

- Participants who complete the open-label treatment phase on study drug and do not continue on any MS DMT.
- Participants who prematurely discontinue study drug and study participation, and do not continue on any MS DMT.

All safety follow-up period visits are scheduled relative to the End of Study (EOS) visit.

All participants who elect to not be included in the 12-month extension will be followed for an additional 100 days following the EOS timing for that individual participant. A shorter follow-up time is acceptable if participants select a different approved MS DMT (injectable, infusion or oral) treatment during this period. Participants who do not have access to commercial drug within one day of the EOS visit must continue into the safety follow-up period until they are able to access commercial drug or decline DMT treatment moving forward (up to 100 days maximum).

Healthy control participants will not have a safety evaluation post end of study.

[figure not shown]
### Study completion

According to the protocol, study completion is defined as when the last participant finishes their Study Completion or EOS visit and any repeat assessments associated with this EOS visit have been documented and followed-up appropriately by the Investigator, or in the event of an early study termination decision, the date of that decision.

For participants who discontinue study treatment and study participation prematurely for any reason before the end of the open-label treatment phase, an EOS visit must be performed within 7 days of study discontinuation.

The study design schematic is shown in [Figure 1](#).

**Figure 1 Study design**

### Primary analysis time point

The primary analysis time point will be Month 18.

### Interim analysis

[figure not shown]
There will be one interim analysis (IA) after the last participant completes his/her Month 18 (primary analysis time point) visit.

## 1.2 Study objectives, endpoints and estimands

Study objectives and associated endpoints are shown in [Table 1](#).

**Table 1 Study objectives and endpoints**

Objective(s)	Endpoint(s)

Primary Objective(s)
 
 
The primary objective is to explore the impact of ofatumumab on the ability to achieve No Evidence of Disease Activity (NEDA-3) status in treatment-naïve, very early RRMS participants over an 18 month, open-label study period after a re-baseline of MRI at 6 months
 
	
Endpoint(s) for primary objective(s)
 
 
NEDA-3 (relapse-free, 3-month clinical disability progression-free, MRI activity-free) in Months 6 to 18 (yes/no)
 

Secondary Objective(s)
 
 
Evaluate the effect of ofatumumab on various clinical (NEDA, disability, relapse) metrics at 18 months
 
Evaluate the effect of ofatumumab on conventional MRI metrics, with MRIs at Baseline and Months 6, 12, 18, 30 (T1 gadolinium (Gd) @ Baseline, Month 6, 18 and T1/T2 @ every timepoint)
 
Evaluate the effect of ofatumumab on patient reported outcomes (PROs) (Quality of Life in Neurological Disorders [NeuroQOLTM], Patient Determined Disease Steps [PDDS])
 
Evaluate the effect of ofatumumab vs healthy controls on 1) whole brain and regional atrophy measured at Month 18/30 after re-baseline at 6 months; and 2) regional atrophy measured 18/30 months from Baseline
 
Evaluate the safety and tolerability of ofatumumab
 
	
Endpoint(s) for secondary objective(s)
 
 
Number of confirmed relapses in Months 6 to 18
 
3-month disability worsening-free in Months 6 to 18 (yes/no)
 
NEDA clinical in Months 6 to 18 (yes/no)
 
NEDA radiological in Months 6 to 18 (yes/no)
 
Change from baseline in conventional MRI metrics (Gd+ lesion number, new Gd+ lesion number, Gd+ lesion volume, T2 lesion number (Baseline), new/enlarging T2 lesion number (post-Baseline), T2 lesion volume, new/enlarging T2 lesion volume, new unenhancing T1 lesion number, T1 unenhancing lesion volume)
 
Change from baseline in PROs (NeuroQOLTM, PDDS) (also obtained in healthy controls)
 
Brain volume assessment (whole brain and regional) (also obtained in healthy controls)
 
Adverse events, laboratory data, physical examination, and vital signs (also obtained in healthy controls)
 

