• Evaluate the effect of ofatumumab on patient reported outcomes (PROs) (NeuroQOL™, Patient Determined Disease Steps [PDDS])	• Change from Baseline in Patient Reported Outcomes (NeuroQOL™, PDDS) (also obtained in HC)
• Evaluate the effect of ofatumumab vs healthy controls on 1) whole brain and regional atrophy measured at month 18/30 after re-baseline at 6 months; and 2) regional atrophy measured 18/30 months from Baseline	• Brain volume loss (BVL) assessment (whole brain and regional) (also obtained in HC)
• Evaluate the safety and tolerability of ofatumumab	• Adverse events, laboratory data, physical examination, and vital signs (also obtained in HC)

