Collect Study Drug/ Drug Account-ability			O	O	O	O	O	O	O	O	O	O	O	O	O		O

[figure not shown]
Name	Scr	BSL/ Wk0	Wk 1	Wk 2	Wk 4	M3	M6	M9 ⁶	M12	M15 ⁶	M18	M21 ⁶	M24 ⁶	M27 ⁶	M30/ EOS	100- day Safety Follow -up ¹²	USV ⁴
Days: Window:	-28	1 (+3)	7 (±1)	14 (±1)	28 (±3)	90 (±3)	180 (±3)	270 (±3)	360 (±3)	450 (±3)	540 (±3)	630 (±3)	720 (±3)	810 (±3)	900 (±3)		
Sc Self-injection Training (participant and/or caregiver) ^s		O															
Study drug self- injection (at- home or at site) ^x . 16, 17			O	O	O	O	O	O	O	O	O	O	O	O	O		
Prior and Concomitant Meds ^x	O,H	O,H	O,H	O,H	O,H	O,H	O,H	O,H	O,H	O,H	O,H	O,H	O,H	O,H	O,H	O	O,H
Non-drug therapies ^x	O,H	O,H	O,H	O,H	O,H	O,H	O,H	O,H	O,H	O,H	O,H	O,H	O,H	O,H	O,H	O	O,H
Vital Signs ^{x,7}	O,H	O,H	O,H	O,H	O,H	O,H	O,H		O,H		O,H				O,H		O,H
Physical Exam ^s	O ³ ,H	O,H	O,H	O,H	O,H	O,H	O,H		O,H		O,H				O,H		O,H
Adverse Events ^{x,4}	O,H	O,H	O,H	O,H	O,H	O,H	O,H	O,H	O,H	O,H	O,H	O,H	O,H	O,H	O,H	O	O,H

Name	Scr	BSL/ Wk0	Wk 1	Wk 2	Wk 4	M3	M6	M9 ⁶	M12	M15 ⁶	M18	M21 ⁶	M24 ⁶	M27 ⁶	M30/ EOS	100- day Safety Follow -up ¹²	USV ⁴
Days: Window:	-28	1 (+3)	7 (±1)	14 (±1)	28 (±3)	90 (±3)	180 (±3)	270 (±3)	360 (±3)	450 (±3)	540 (±3)	630 (±3)	720 (±3)	810 (±3)	900 (±3)		
MS Relapse Assessment ^{x, 2}	○	○	○	○	○	○	○	○	○	○	○	○	○	○	○	○	○
Labs (hematology, biochemistry) ^x	○										○				○	○	○

Name	Scr	BSL/ Wk0	Wk 1	Wk 2	Wk 4	M3	M6	M9 ⁶	M12	M15 ⁶	M18	M21 ⁶	M24 ⁶	M27 ⁶	M30/ EOS	100- day Safety Follow -up ¹²	USV ⁴
Days: Window:	-28	1 (+3)	7 (±1)	14 (±1)	28 (±3)	90 (±3)	180 (±3)	270 (±3)	360 (±3)	450 (±3)	540 (±3)	630 (±3)	720 (±3)	810 (±3)	900 (±3)		
Hepatitis B ^{S, 9}	O																
HIVs, ⁹	O																
Coagulation ^{S, 9}	O	O									O				O		O
Dipstick urinalysis ^{X, 10}	O	O									O				O		O
Serum β-hCG in women of childbearing potential ^{S, 3}	O	O															O
Urine β-hCG in women of childbearing potential ^{S, 3}			O	O	O	O	O	O	O	O	O	O	O	O	O		O
MRI ^{X, 14, 18}	O,H						O,H		O,H		O,H				O,H		O
Columbia Suicide Severity Scale (C- SSRS) ^{X, 15}	O	O	O	O	O	O	O		O		O				O		
PROs ^X (NeuroQOL™, PDDS)		O,H	O,H	O,H	O,H	O,H	O,H		O,H		O,H				O,H		

Name	Scr	BSL/ Wk0	Wk 1	Wk 2	Wk 4	M3	M6	M9 ⁶	M12	M15 ⁶	M18	M21 ⁶	M24 ⁶	M27 ⁶	M30/ EOS	100- day Safety Follow -up ¹²	USV ⁴
Days: Window:	-28	1 (+3)	7 (±1)	14 (±1)	28 (±3)	90 (±3)	180 (±3)	270 (±3)	360 (±3)	450 (±3)	540 (±3)	630 (±3)	720 (±3)	810 (±3)	900 (±3)		
Optional Trial Feedback Questionnaire ^S		O,H					O,H				O,H				O,H		
Participant Thank You Letter ^S		O,H									O,H				O,H		

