O = Ofatumumab participant

H = Healthy Control

X = assessment to be recorded in the clinical database or received electronically from a vendor

S = assessment to be recorded in the source documentation only

■ [Redacted]

² Relapse assessment will be performed in scheduled, as well as unscheduled visits as deemed necessary by the Investigator or designee. Assessment can be done on site or via remote procedures

³ Urine β-hCG will be conducted monthly, at home, as well as, at defined clinical visits (scheduled and unscheduled)

[Redacted]

⁴ Assessment during an unscheduled visit will be performed as deemed necessary by the investigator, **except** for vital signs and evaluation of AE, which are mandatory at each visit

⁶ Participants are not required to come to the study site. Remote contact with participants, by site staff around the time of at-home, self-administration of ofatumumab should query about any new or worsening symptoms warranting an unscheduled visit, MS relapse, compliance with study treatment [REDACTED], adverse events, and compliance with contraception requirements (when applicable). The method of contact can be via telephone, email, video conference or text message depending on the preference of each participant

⁷ For the first injection, vital signs should be obtained 30-60 minutes before sc injection and again approximately 60 minutes post-injection

⁸ All lab assessments should be taken prior to dosing at the Day 1 visit. For any later biomarker visits, if the visit coincides with the day the monthly injection is scheduled, the subject should not take the injection in the morning before coming to the site so that the biomarker sample can be drawn before the injection

⁹ Labs must be drawn to allow adequate time for results to be obtained before first study drug administration to ensure participant's eligibility

¹⁰ Urine dipstick: If abnormal send full urinalysis to central laboratory

¹² Data for safety follow-up visit will be captured in source documentation only. Safety follow-up participants are not required to come to study site and lab assessments should be done locally

¹³ Only for participants continuing onto the 12-month open-label extension period

¹⁴ Gadolinium will not be given to healthy controls and gadolinium enhanced T1 MRI imaging will not be conducted in healthy controls

¹⁵ The C-SSRS must be administered at either screening or baseline, then at every on-site visit thereafter until End of Study (EOS)

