8.4.3 Columbia Suicide Severity Rating Scale (C-SSRS)

The C-SSRS is a questionnaire that prospectively assesses suicidal ideation and suicidal behavior. The C-SSRS must be administered at either Screening or Baseline/week 0 (day 1), then at every on-site visit thereafter until end of study (EOS).

The electronic version of the C-SSRS (eC-SSRS) will be administered by the Investigator. A completed pC-SSRS must be filed in the participant's source documents.

If, at any time after Screening, the score is "yes" on item 4 or item 5 of the suicidal ideation section of the C-SSRS or "yes" on any item of the suicidal behavior section, the participant must be referred to a mental healthcare professional for further assessment and/or treatment. The decision on whether the study drug should be discontinued is to be taken by the Investigator in consultation with the mental health professional to whom the participant is referred.

In addition, all life-threatening events must be reported as SAEs. For example, if a participant answers "yes" to one of the questions in the suicidal behavior section, an SAE must be reported if the event was life-threatening. All events of "Non-Suicidal Self-Injurious Behavior" (question also included in the suicidal behavior section) should be reported as AEs and assigned the appropriate severity grade.

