10.1 Definition of adverse events and reporting requirements

10.1.1 Adverse events

An adverse event (AE) is any untoward medical occurrence (e.g. any unfavorable and unintended sign [including abnormal laboratory findings], symptom or disease) in a clinical investigation participant after providing written informed consent for participation in the study.

Therefore, an AE may or may not be temporally or causally associated with the use of a medicinal (investigational) product.

The investigator has the responsibility for managing the safety of individual participant and identifying adverse events.

Novartis qualified medical personnel will be readily available to advise on trial related medical questions or problems.

The occurrence of adverse events must be sought by non-directive questioning of the participant at each visit during the study. Adverse events also may be detected when they are volunteered by the participant during or between visits or through physical examination findings, laboratory test findings, or other assessments.

Abnormal laboratory values or test results constitute adverse events only if they fulfill at least one of the following criteria:

- they induce clinical signs or symptoms
- they are considered clinically significant
- they require therapy

Clinically significant abnormal laboratory values or test results must be identified through a review of values outside of normal ranges/clinically notable ranges, significant changes from baseline or the previous visit, or values which are considered to be non-typical in participants with the underlying disease. Clinically notable laboratory findings are defined according to the Common Terminology Criteria for Adverse Events (CTCAE; the most current version will be used and can be found on the following website: ctep.cancer.gov).

Adverse events must be recorded under the signs, symptoms, or diagnosis associated with them, accompanied by the following information (as far as possible) (if the event is serious refer to [Section 10.1.2](#)):

1. The CTCAE grade (based on most current version)

If CTCAE grading does not exist for an adverse event, use:

- 1 = mild: usually transient in nature and generally not interfering with normal activities
- 2 = moderate: sufficiently discomforting to interfere with normal activities
- 3 = severe: prevents normal activities
- 4 = life-threatening
- 5 = death

2. Its relationship to the study treatment.

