### **2.7.1 Adverse events (AEs)**

Adverse events (AEs) will be coded using MedDRA terminology. The MedDRA version used for reporting the study will be indicated in a footnote on relevant outputs.

For reporting purposes, summary tables for AEs will summarize only the following events for ofatumumab-treated participants and healthy control participants:

- On-treatment events (treatment-emergent AEs), which started or worsened on or after the date of the first dose of ofatumumab for ofatumumab-treated participants
- On-study events, which started or worsened on or after the date of the date of Week 0 visit for healthy control participants

The number and percentage of participants with treatment-emergent/on-study AEs will be summarized for the open-label treatment phase, open-label extension period and overall, in the following ways using the SAF or HCAS, as appropriate:

- by Cohort, primary SOC and PT
- by Cohort, primary SOC, PT and maximum severity
- by Cohort and PT

Separate summaries will be provided using the SAF or HCAS, as appropriate, for treatment-emergent/on-study AEs occurring with a frequency of >5% in either Cohort, treatment-related AEs (only applicable to ofatumumab-treated participants), AEs leading to study drug interruptions (only applicable to ofatumumab-treated participants), serious adverse events (SAEs), treatment-related SAEs (only applicable to ofatumumab-treated participants) and other significant AEs leading to discontinuation.

In addition, an overview of treatment-emergent/on-study AEs will be summarized for the open-label treatment phase, open-label extension period and overall, presenting the number and percentage of participants having at least one AE for each of the categories described above.

If a participant reported more than one AE with the same PT, the AE with the greatest severity will be presented. A participant with multiple AEs within a primary SOC is only counted once towards the total of the primary SOC.

Partial AE start and end dates will be imputed as outlined in [Section 5.1.2](#).

For the legal requirements of ClinicalTrials.gov and EudraCT, two required tables on on-treatment/treatment-emergent AEs which are not SAEs with an incidence greater than 5% and

on on-treatment/treatment-emergent SAEs and SAEs suspected to be related to study treatment will be provided by SOC and PT on the SAF.

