### **2.7.3 Laboratory data**

Shift tables using the low/normal/high/ (low and high) classification will be used to compare baseline to the worst on-treatment value for hematology and chemistry parameters using the SAF. In particular, the number and percentage of participants with laboratory values will be presented by low/normal/high/ (low and high) classifications to compare baseline to worst on-treatment value for the open-label treatment phase, open-label extension period and overall. Unscheduled assessments will be considered.

Values and changes from baseline in hematology and chemistry parameters will be summarized by time point with descriptive statistics using the SAF.

Laboratory abnormalities will be flagged in listings.

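### The endpoint tables list laboratory data as also obtained in healthy controls, but every visible safety-lab row of the schedule is ofatumumab only, so test-detected AEs are found somewhat unequally in the by-cohort AE tables

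*SAP*

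**What the plan says.** Both endpoint tables put laboratory data among the safety measures shared with healthy controls. SAP Table 1 has "Adverse events, laboratory data, physical examination, and vital signs (also obtained in healthy controls" and Protocol Table 2-1 has "Adverse events, laboratory data, physical examination, and vital signs (also obtained in HC".

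The assessment schedule (Protocol Table 8-1) marks each cell by cohort, with the key "O = Ofatumumab participant" and H for healthy control. The row "Labs (hematology, biochemistry", closed by a bracket in the table, has no H in any column, including unscheduled visits. The coagulation, dipstick urinalysis and C-SSRS rows have no H either. The rows for adverse events, vital signs and physical examination carry both letters.

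The body of the SAP follows the schedule rather than its own Table 1. Section 2.7.3 says "Values and changes from baseline in hematology and chemistry parameters will be summarized by time point with descriptive statistics using the SAF". Section 2.7.4.3 also places the C-SSRS on the safety set (SAF). Vital signs (2.7.4.1) are summarised by cohort on the SAF or the healthy control set.

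On sources of AEs, Protocol 10.1.1 says "Adverse events also may be detected when they are volunteered by the participant during or between visits or through physical examination findings, laboratory test findings," and goes on to name other assessments. Protocol 8.4.3 says that non-suicidal self-injurious behaviour, which the C-SSRS asks about, "should be reported as AEs and assigned the appropriate severity grade". SAP 2.7.1 tabulates AEs "by Cohort, primary SOC and PT", with a list of AEs above 5% in either cohort and an overview of participants with at least one AE.

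**The concern.** A reader of either endpoint table would expect a control benchmark for the safety laboratory data, and neither the visible schedule nor the SAP analysis supplies one.

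The AE tables carry a second effect. The Protocol summary names adverse events among the outcomes to be compared with healthy controls. An event found only by a blood test, a dipstick or a C-SSRS question has a scheduled route into the ofatumumab column and none into the control column. For such terms a low control percentage partly reflects absence of testing, and SAP 2.7.1 does not say so. Infections are the safety example that Protocol 1.2 and 4.1 give for the control comparison. They are not wholly exempt: the ofatumumab-only dipstick includes white cells and nitrite (Protocol Table 8-4), and all infections are reported as AEs (Protocol 16.1.2).

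**Working it through.** **Step 1: count the schedule.** The plan gives no figure to reproduce on this point. Scheduled post-baseline occasions up to and including Month 18, from Protocol Table 8-1:

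| Assessment | Visits | Ofatumumab | Control |
|---|---|---|---|
| Hematology/biochemistry | M18 | 1 | 0 |
| Coagulation | M18 | 1 | 0 |
| Dipstick urinalysis | M18 | 1 | 0 |
| C-SSRS | Wk1, Wk2, Wk4, M3, M6, M12, M18 | 7 | 0 |
| AE enquiry | Wk1, Wk2, Wk4, M3, M6, M9, M12, M15, M18 | 9 | 9 |
| Vital signs | Wk1, Wk2, Wk4, M3, M6, M12, M18 | 7 | 7 |
| Physical examination | as for vital signs | 7 | 7 |

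At unscheduled visits, the three laboratory rows are again ofatumumab only, while AE enquiry, vital signs and physical examination are marked for both cohorts.

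**Step 2: any-AE percentage.** The documents give no AE rates, so these are assumptions. Let p be the share of each cohort with an AE found by the shared routes, equal in both. Let q be the share of the remaining ofatumumab participants whose only AE is found by labs, urinalysis, coagulation or C-SSRS. If no such AE is ever found in controls, the artificial difference is

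[1 − (1 − p)(1 − q)] − p = (1 − p)q.

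For scale, the 95% half-width of a difference between 118 and 50 participants at a common p is 1.96 × √[p(1 − p)(1/118 + 1/50)].

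| p | q = 2% | q = 5% | q = 10% | Half-width |
|---|---|---|---|---|
| 30% | 1.4 points | 3.5 | 7.0 | 15.2 |
| 60% | 0.8 | 2.0 | 4.0 | 16.2 |
| 80% | 0.4 | 1.0 | 2.0 | 13.2 |

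The range is 0.4 to 7.0 points, below the half-width in every row.

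**Step 3: single terms.** Six of 118 is 5.1%, enough for the above-5% list; five of 118 is 4.2%, which is not. If a purely test-detected event truly affected 5% of both cohorts, 118 × 0.05 = 5.9 ofatumumab participants and 50 × 0.05 = 2.5 controls would have it. No scheduled test would look for the 2.5. The distortion is proportionally larger here than in the any-AE row.

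**The case against.** The strongest case on the other side is that this is a wording slip with little effect on the analysis. The SAP's working sections are clear that laboratory data and C-SSRS are analysed in ofatumumab participants only. No control laboratory table is planned that could be misread. The AE tables are descriptive, with no hypothesis test. The cohorts already differ by disease and by monthly injections, so the any-AE gap was never a clean drug effect. Much of this stands, and it limits the size of the point. It does not correct the endpoint line, and it does not tell a reader of the AE tables that testing differed.

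Four stronger readings are tempting, and the documents do not support them.

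- A reader might infer that no laboratory data of any kind exist for controls. Controls must be able to give blood (Protocol 5.1, criterion 4), and Table 8-1 appears to have redacted rows: its footnote 8, on laboratory and biomarker sampling, attaches to no visible row. What can be said is that no visible safety-lab row includes controls.
- A reader might infer that control figures for test-based terms are zero by construction. Under Protocol 10.1.1 an abnormal result is an AE only if it causes signs or symptoms, is clinically significant or needs therapy. The first and last kinds can surface in controls through AE questioning or concomitant medication records, and findings from outside care can be volunteered. Mainly symptomless, untreated but clinically significant findings are missed.
- A reader might infer that the C-SSRS contradicts the endpoint line. It is not named there. For the C-SSRS the point is unequal ascertainment only.
- A reader might infer a large bias against ofatumumab. The rates needed for that have no basis in the documents, and the main AE routes are scheduled equally.

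**Conclusion.** The inconsistency is established: both endpoint tables claim control laboratory data under the safety objective, while the visible schedule and SAP 2.7.3 do not provide them. Unequal detection in the by-cohort AE tables follows from the plan's own text. It is confined mainly to terms found through laboratory tests, urinalysis or the C-SSRS.

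Its size cannot be fixed from the documents. The 0.4 to 7.0 points for any AE assume shared-route AE rates of 30 to 80%, equal in both cohorts, test-only AEs in 2 to 10% of the remaining ofatumumab participants, and none of these ever found in controls. With a single scheduled post-baseline laboratory draw by Month 18, the effect is probably small for any AE and more noticeable for individual test-detected terms. The primary endpoint is not affected.

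**What to change.** 1. In SAP Table 1 and Protocol Table 2-1, remove laboratory data from the measures described as also obtained in healthy controls. If control safety labs are in fact collected, correct Table 8-1 and SAP 2.7.3 instead. The sponsor knows which applies.
2. In SAP 2.7.1, keep the full by-cohort AE tables for both cohorts. State on them that safety labs, urinalysis, coagulation and C-SSRS were scheduled only in ofatumumab participants, so control figures for terms found that way are not an observed benchmark.
3. Add one supplementary by-cohort any-AE summary that excludes laboratory-investigation terms and self-injury or suicidality terms in both cohorts, with the term list fixed before the data are analysed.

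The listed preferred terms should not be moved into an ofatumumab-only block. A preferred term does not show how an event was found, so that layout would hide real control events and take possibly drug-related terms out of the comparison. The supplementary summary also drops some clinically detected events, which is why it should sit beside the full tables and not replace them.

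The cost is a wording change in two tables, a footnote, a short term list and one extra descriptive table. No added control procedures are needed.
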